Academic Institution	Name: [name] Address: Manchester Metropolitan University, [name] Contact no: [name]

[figure not shown]
STUDY SUMMARY

Full study title	A comparative assessment of the relationship between the measurements made in an incremental shuttle walk test and an incremental cycle ergometry test in patients with idiopathic pulmonary fibrosis	
Short study title	ISWT vs CPET	
Study aim	
 1. To test the relationship between VO_2 peak in a CPET and the distance walked in an ISWT 2. To test the hypothesis that PO_2 is the same at the end of an ISWT and a CPET. 	
Study design	Single centre	
Study participants	Patients over the age of 16 with a confirmed diagnosis of IPF	
Study arms	Not applicable	
Sample size	43	
Planned study period	4 months	
Planned recruitment start date	1 st December 2017	
Planned recruitment end date	1 st March 2018	
Planned study end date	31 st March 2018	
	Objectives	Outcome Measures
Primary	To test the relationship between distance walked in an ISWT and VO_2 peak measured in a CPET.	VO_2 peak

Key Words: Idiopathic pulmonary fibrosis, cardiopulmonary exercise test, incremental shuttle walk test, VO_2 peak

STUDY FLOW CHART

Figure 1: Flow of participants through the study

SCHEDULE OF OBSERVATIONS

Table 1: Schedule of measures:

Schedule of events

Procedure	First meeting	Phone conversation	Second meeting	Visit one	Visit two
Eligibility Check	X				
Decision to take part in study or not to take part in study		X			
Informed consent			X		
Participant questionnaire			X		
Incremental shuttle walk test				X ^A	X ^B
Cardiopulmonary exercise test				X ^B	X ^A
Capillary blood gas				X	X

X – applies to all patients, whether in group A or group B.

X^A – patient randomly assigned to group A. These patients complete the ISWT at visit one and CPET at visit two.

X^B – patient randomly assigned to group B. These patients undertake CPET at visit one and ISWT at visit two.

LIST of CONTENTS

GENERAL INFORMATION	Page No.
TITLE PAGE	1
RESEARCH REFERENCE NUMBERS	1
SIGNATURE PAGE	2
KEY TRIAL CONTACTS	3
TRIAL SUMMARY	4
TRIAL FLOW CHART	5
SCHEDULE OF OBSERVATIONS	6
LIST OF CONTENTS	7
LIST OF ABBREVIATIONS	8
SECTION	
1. INTRODUCTION	9
2. TRIAL DESIGN	13
3. STUDY SETTING	13
4. ELIGIBILITY CRITERIA	14
5. TRIAL PROCEDURES	15
6. STATISTICS AND DATA ANALYSIS	16
7. DATA HANDLING	17
8. TRIAL OVERSIGHT	18
9. MONITORING, AUDIT & INSPECTION	18

1. INTRODUCTION

Idiopathic pulmonary fibrosis (IPF) is a chronic and fatal lung disease. As IPF progresses, patients become increasingly breathless with reduced exercise capacity and quality of life. Average life expectancy is three years from diagnosis but IPF progresses at different rates in different people. In 2012 the British Lung Foundation estimated that 32,500 in the UK had IPF.

An accurate prognosis can help determine the most appropriate treatment option and allow patients and their families to make suitable plans. Currently, measurements made during resting lung function tests are used to predict prognosis. However, evidence suggests that measurements made during a cardiopulmonary exercise test (CPET), particularly peak oxygen consumption (VO_2 peak) are more sensitive predictors of survival. CPET is the gold standard for assessing IPF but has not been adopted in clinical practice.

The incremental shuttle walk test (ISWT) is quicker, cheaper and more widely available than CPET. This study builds on previous research from our department which showed a relationship between the distance walked in an ISWT and VO_2 peak during a CPET. We will identify any relationship between ISWT distance and VO_2 peak in a new cohort of patients and compare this with the relationship of the previous study. Patients will undertake both ISWT and CPET and the results will be compared. This study paves the way for a simple, standardised test to more accurately predict prognosis in IPF.

1.1 Background

IPF is a chronic, progressive lung disease of unknown cause characterised by uncontrolled fibrosis of the lung interstitium. IPF causes progressive lung function decline, exercise limitation, reduced quality of life and ultimately death (NICE, 2013b; Miki et al., 2003). Life expectancy is approximately three to four years from the time of diagnosis though there is much variation between individuals (King et al., 2001; Navaratnam et al., 2011; Gribbin et al., 2006). Over 5000 people are diagnosed with IPF each year in the UK with an estimated 5% increase in incidence year-on-year since 1968 (Navaratnam et al., 2011).

ISWT vs CPET

Patients with IPF may be referred for lung transplantation. Alternatively, disease management options focus on slowing progression and maintaining quality of life. These include symptom relief, management of comorbidities, withdrawal of ineffective or harmful therapies and palliative care (NICE, 2013b). Two pharmacological therapies, Pirfenidone and Nintedanib, are licensed for the treatment of IPF for the purpose of slowing disease progression (NICE, 2013a; NICE, 2016).

IPF progresses at different rates in different individuals (Travis et al., 2013). This has led to calls for a validated scoring system to predict a patient's likely prognosis using clinical tests (Swigris et al., 2005; Ley et al., 2011). Similar scoring systems are already recommended for patients with chronic obstructive pulmonary disease (NICE, 2010). An accurate prognosis informs selection of the most suitable treatment and allows patients, their families and their care providers to make appropriate plans (Raghu et al., 2011; Swigris et al., 2005). Prognostic models are also useful in therapeutic trials for making baseline comparisons between individuals assigned to different treatment groups and including prognostic variables in analyses (Swigris et al., 2005).

Current NICE guidelines (2013b) for IPF management recommend using resting measurements of spirometry and gas transfer to assess disease severity and likely prognosis. However, patients with IPF demonstrate significant exercise limitation due to impaired gas exchange and ventilation (Miki et al., 2003). Measurements made during exercise have been shown to be more sensitive to the changes in oxygen transfer associated with IPF than those made at rest (Ley et al. 2011). CPET is recognised as a gold standard test for IPF assessment but has not been routinely adopted in practice (Bonini and Fiorenzano, 2017).

A study of IPF by Kawut et al. (2005) showed that VO_2 peak in a maximal CPET was inversely proportional to a patient's risk of death. Similarly, Fell et al. (2009) found that a VO_2 peak of < 8.3 ml/kg/min in a CPET was associated with an increased risk of death in patients with IPF. Oxygen consumption during an incremental treadmill test and an ISWT increases similarly (Singh et al., 1994) and, because an ISWT is cheaper, quicker and easier to perform, the usefulness of measurements made during an ISWT should be evaluated in more detail.

Moloney et al. (2003) demonstrated a significant correlation between total distance walked in a corridor ISWT by patients with IPF and the VO_2 max measured during a shuttle walk test on a treadmill. In a previous study in our department the distance walked in an ISWT by patients diagnosed with IPF

ISWT vs CPET

correlated with the individual's VO_2 peak during an incremental cycle ergometry test (ICET) (Fielding et al., 2015). Linear regression was used to derive a formula which predicted VO_2 peak using ISWT distance. The present study looks to test this formula in a new cohort of patients with IPF.

Arterial oxygen pressure (PaO_2) at the end of a maximal CPET has also been shown to be a significant predictor of survival in patients with IPF (King et al., 2001). This study also investigates the relationship between blood oxygen pressure (PO_2) at the end of a CPET and the end of an ISWT.

1.2 Proposed study

Patients at University Hospital, Coventry and St Cross Hospital, Rugby will be invited to take part in a letter. Those who express an interest in taking part will be given more information about the study including a written document and then at least 48 hours to decide whether or not to take part in the study. Should they decide to take part, each participant will be asked to make two visits to University Hospital Respiratory Physiology and Sleep Department.

At one visit participants will be asked to undertake an ISWT; walking 10 m between cones at an increasing speed dictated by a standardised audiotape. The ISWT will be performed according to the standardised protocol set out by Singh et al. (1992) and our department protocol. At the other visit participants will undertake an ICET. The ICET will be performed on a static exercise bike following the department protocol. The order in which these two tests are done will be randomly assigned to each participant.

After both the ISWT and the ICET, an earlobe capillary blood sample will be taken by a trained member of staff and the sample analysed for blood oxygen pressure. Each participant will also fill in a questionnaire about their experience of the test.

The relationship between ISWT distance and VO_2 peak will be analysed and the oxygen pressure of capillary blood gas after each test will be compared.

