1.3 Study population

This is a prospective study of patients with a diagnosis of IPF confirmed by a multi-disciplinary team. We aim to recruit a minimum of 43 patients to this study, all of whom will already be under the care of a Respiratory Consultant at University Hospitals Coventry and Warwickshire NHS Trust.

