1 RATIONALE

2.1 Aims and hypothesis

- To test the relationship between VO_2 peak and the distance walked in an ISWT
- To test the hypothesis that PO_2 is the same at the end of an ISWT and a CPET.

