7.5 Statistical analysis

The data collected in this study will be combined with data from the previous study in our department and distinguished by a study indicator. The similarity between the two datasets will be tested using a series of linear regression models. The value of PO₂, measured in capillary blood, after ISWT and after CPET will be compared using a paired t-test. All analyses will be performed in SPSS statistical software. We do not anticipate missing data. Should a participant withdraw from the study then none of the identifiable data that they generated will be used.

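### The paired t-test for PO2 ignores the randomised test order, so any difference between visits costs power and shifts the estimate when the order groups are unequal

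*Combined protocol and SAP*

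**What the plan says.** The second aim in section 2.1 is: "To test the hypothesis that PO_2 is the same at the end of an ISWT and a CPET". Each patient takes one test at each of two visits, and section 1.2 adds: "The order in which these two tests are done will be randomly assigned to each participant". Table 1 in the schedule of observations defines the two orders. Of group A it says: "These patients complete the ISWT at visit one and CPET at visit two". Group B does the reverse, and capillary blood gas is taken at both visits.

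Section 7.5 gives the only PO2 analysis: the values "measured in capillary blood, after ISWT and after CPET will be compared using a paired t-test". The regression models in the same section compare this cohort with the department's previous one and are not described for PO2. No section gives an order, visit or sequence term, an allocation ratio, or a method of randomisation. Section 1.3 sets the size: "We aim to recruit a minimum of 43 patients to this study".

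**The concern.** The design randomises a factor that the analysis leaves out. PO2 may differ between visit one and visit two whatever the test, for example through familiarity with exercise testing or a change in the patient's condition. The ISWT-minus-CPET difference would then be centred at different values in groups A and B. A plain paired t-test treats that separation as random scatter.

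This matters because the paired t-test is the only test of one of the study's two aims, and the hypothesis is one of no difference. A test that has lost power is more likely to give a non-significant result, which a reader could take as support for the hypothesis. If the order groups are unequal, the estimate also absorbs part of the visit effect.

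**Working it through.** **Inputs.** From the documents: N = 43 (section 1.3), two order groups (Table 1), paired t-test (section 7.5). The documents give no PO2 difference, SD, alpha, power, visit effect or allocation ratio, so there is no PO2 power figure to reproduce. Assumed: two-sided alpha of 5%; within-group SD of the paired difference s = 1; visit effect d (visit one minus visit two) of 0.25, 0.5 or 1 in units of s. The true difference is set at 0.437, which gives the paired t-test 80% power at N = 43 when d = 0 (noncentral t, 42 df).

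**Model.** Let tau be the true ISWT-minus-CPET difference. The paired difference has mean tau + d in group A and tau − d in group B. Pooling the groups gives:

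- Expected estimate = tau + d(nA − nB)/N. The shift is d × 1/43 = 0.023d at 22/21 and d × 9/43 = 0.209d at 26/17.
- Variance of the pooled differences = 1 + 4(nA·nB/N²)d². At 22/21, 4 × 462/1849 = 0.9995, so the SD is √(1 + 0.9995d²).
- Equivalent sample size = 43 divided by that variance, for example 43/1.250 = 34.4 at d = 0.5.

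**Results for the paired t-test** (power and type I error from simulation, 160,000 runs per cell):

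| d | SD inflation, 22/21 | Equivalent n, 22/21 | Power, 22/21 (shift toward / away from zero) | Type I error, 22/21 | Type I error, 26/17 | Power averaged over simple randomisation |
|---|---|---|---|---|---|---|
| 0.25 | 1.031 | 40.5 | 77.1% / 79.4% | 4.3% | 5.6% | 77.7% |
| 0.5 | 1.118 | 34.4 | 70.0% / 75.1% | 3.0% | 6.8% | 70.8% |
| 1 | 1.414 | 21.5 | 44.6% / 56.3% | 0.6% | 8.0% | 50.4% |

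Averaged over simple randomisation, type I error is 5.0–5.1%. At 26/17 with the shift toward zero, power is about 67%, 48% and 10%. A second simulation (40,000 runs per cell) gave matching power: 78.9%, 75.2% and 56.4% at 22/21 with the shift away from zero, and 77.7%, 70.7% and 50.6% under simple randomisation.

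**How likely is an uneven split?** If exactly 43 patients are allocated by simple 1:1 randomisation, the chance that the smaller group has 17 or fewer is 0.222 (binomial).

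**Order-adjusted analysis.** The estimate is the unweighted mean of the two group means, with SE = 0.5 × √(1/nA + 1/nB) on 41 df. This is 0.5 × √(1/22 + 1/21) = 0.1525 at 22/21 and 0.5 × √(1/26 + 1/17) = 0.1560 at 26/17. The paired t-test with d = 0 has 1/√43 = 0.1525. Adjusted power is 79.9% and 78.2% whatever the value of d, and simulated type I error is 4.9–5.1% in every cell.

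**The case against.** The strongest reply is that the planned test is valid. Randomising the order already removes systematic bias: over all randomisations the estimate is centred on the true difference and type I error is 5%. With no visit effect nothing is lost. No treatment is given between visits, both visits are in the same department, and nothing in the documents points to a visit effect, still less one as large as the whole SD of the paired differences. At d = 0.25 and a near-even split the loss is only 1–3 points. Type I error above 5% needs both a visit effect and an uneven split; near balance the test is conservative. The 80% baseline is constructed, because the plan sets no power target for PO2. PO2 is also missing from the objectives and endpoints in section 3, which list only VO2 peak.

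All of this is correct, and it limits the weight of the point. It does not justify leaving order out. The plan neither states nor argues that there is no visit effect. Validity averaged over randomisations does not recover the lost power, and it does not correct the estimate for the split actually obtained. PO2 remains one of two stated aims, and this is its only test. The relative loss of information (equivalent n of 40.5, 34.4 and 21.5) depends on d and the split, not on the constructed 80% baseline.

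**Conclusion.** The concern holds. The PO2 comparison is a two-period crossover analysed without the order it randomises. The cost depends on a visit effect that the documents do not quantify: 1–3 points of power at 0.25 SD, 5–10 at 0.5 SD and 24–35 at 1 SD, near balance and against a constructed 80% baseline. At a 26/17 split, type I error rises to 5.6–8.0% over the same range. That split or worse has a 22% chance if simple randomisation is used, which is an assumption. With no visit effect there is no harm.

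This should be changed because the remedy is nearly free, not because the planned test is invalid. It affects the second aim only. It does not supply a margin for concluding that the two PO2 values are the same, which is a separate matter.

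**What to change.** In section 7.5, replace the paired t-test for PO2 with the standard two-period crossover analysis. Regress each patient's ISWT-minus-CPET PO2 difference on order group, coded +1 for A and −1 for B, and report the intercept with its 95% CI as the difference between tests. With complete pairs, a mixed model with test and visit as fixed effects and patient as a random effect gives the same estimate. State that the adjustment does not deal with carry-over that differs between the two orders.

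As a refinement, state that order is allocated 1:1 in permuted blocks, which keeps the groups close to equal. The order term works without it.

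The cost is one or two sentences and one model term in the software already named, with no extra patients, visits or data. One degree of freedom is lost (42 to 41). With no visit effect, power goes from 80.0% to 79.9% at 22/21 and to 78.2% at 26/17.

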1.3 Study population

This is a prospective study of patients with a diagnosis of IPF confirmed by a multi-disciplinary team. We aim to recruit a minimum of 43 patients to this study, all of whom will already be under the care of a Respiratory Consultant at University Hospitals Coventry and Warwickshire NHS Trust.

1 RATIONALE

2.1 Aims and hypothesis

- To test the relationship between VO_2 peak and the distance walked in an ISWT
- To test the hypothesis that PO_2 is the same at the end of an ISWT and a CPET.

2.2 Justification

This project tests a formula proposed by Fielding et al. (2015) to predict VO_2 peak during an ICET using distance walked in an ISWT. It will compare predicted VO_2 peak value with the actual value in a new cohort of patients with IPF. In addition, this study will test the relationship between PO_2 at the end of an ICET and at the end of an ISWT.

NICE recognises the importance of providing patients and their families with information when IPF is diagnosed and as the disease progresses (NICE, 2013b). Patients can be better informed about expectations of future symptoms and management, their treatment options and their life expectancy if more accurate prognostic tests are available.

This study paves the way for a relatively cheap and widely available incremental exercise test to be used to gather helpful information about a patient's prognosis. In the future, such a test could be recommended for making prognostic predictions in IPF.

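### The PO2 question is worded in two ways, and the only PO2 analysis, a paired t-test, can neither describe the relationship between the two values nor establish that they are the same

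*Combined protocol and SAP*

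**What the plan says.** The protocol states its PO2 question in two ways.

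- **Sameness.** Section 2.1 (Aims and hypothesis), matching the Study Summary: "To test the hypothesis that PO_2 is the same at the end of an ISWT and a CPET". Section 1.2 (Proposed study) is close to this: "the oxygen pressure of capillary blood gas after each test will be compared".
- **Relationship.** Section 1.1 (Background): "This study also investigates the relationship between blood oxygen pressure (PO_2) at the end of a CPET and the end of an ISWT". Section 2.2 (Justification): "this study will test the relationship between PO_2 at the end of an ICET and at the end of an ISWT".

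The documents use ICET and CPET for the same cycle test.

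Section 7.5 (Statistical analysis) gives one PO2 analysis: the values "measured in capillary blood, after ISWT and after CPET will be compared using a paired t-test". The other analysis in that section is "The similarity between the two datasets will be tested using a series of linear regression models". It concerns the new cohort against the department's previous study and does not mention PO2. No correlation, regression, limits of agreement or equivalence margin for PO2 appears anywhere in the document.

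**The concern.** A paired t-test asks whether the average of the within-patient differences is zero. That is one feature of how two measurements compare. It carries no information on whether a patient with a low PO2 after the walk also has a low PO2 after the cycle test, or on how large the difference can be in one patient. Those are the natural meanings of a relationship between the two values. The protocol uses the same word for ISWT distance and VO2 peak, where it means a regression line (section 3.1).

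The sameness wording is not fully served either. Failing to reject a zero mean difference is not evidence that the difference is small, and no acceptable difference is stated.

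Two things are at stake. A question raised in sections 1.1 and 2.2 would go unanswered although the data for it are collected. And a non-significant t-test could be reported as showing that PO2 is the same after both tests, whatever happens in individual patients.

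**Working it through.** **Inputs.** The number of pairs is n = 43, the Study Summary figure, which sections 1.3 and 6 call a minimum; I assume that all pairs are complete. The documents give no alpha, power, SD, correlation or acceptable difference for PO2 and no derivation of 43, so there is no figure of the plan's own to reproduce. I assume two-sided alpha 0.05, bivariate normal values, the same between-patient SD after each test (the unit below), and a range of correlations ρ.

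**1. Spread of individual differences.** SD of differences = √(2(1 − ρ)); 95% limits of agreement = mean difference ± 1.96 × that SD.

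- ρ = 0: √2 = 1.414; 1.96 × 1.414 = ±2.77 SD.
- ρ = 0.9: √0.2 = 0.447; 1.96 × 0.447 = ±0.88 SD.

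**2. What the t-test reports when the true means are equal.** Simulation with n = 43 and 40,000 replicates per setting:

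| ρ | t-test rejects | 95% limits of agreement |
|---|---|---|
| −0.5 | 5.0% | ±3.39 SD |
| 0 | 4.9% | ±2.77 SD |
| 0.5 | 4.9% | ±1.96 SD |
| 0.9 | 5.1% | ±0.88 SD |

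The rejection rate is the nominal 5% throughout. The test returns the same answer whether the values are unrelated or track closely.

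**3. What it reports when there is a fixed mean shift.** For a shift of 0.25 SD, the expected size of the test statistic is about 0.25 × √43 ÷ SD of differences.

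- ρ = 0: 0.25 × 6.557 ÷ 1.414 = 1.16; simulated rejection 20%.
- ρ = 0.9: 0.25 × 6.557 ÷ 0.447 = 3.67; simulated rejection 95%.

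For the same non-zero shift, poorer tracking makes it less likely that the test declares a difference.

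**4. What 43 pairs could deliver if the analyses were added.** With t(0.975, 42) = 2.018:

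- 95% CI for the mean difference: 2.018 ÷ √43 = ±0.31 SD of the differences.
- 95% CI for each limit of agreement: 2.018 × √(1/43 + 1.96² ÷ (2 × 42)) = 2.018 × 0.263 = ±0.53 SD of the differences.
- 95% CI for an observed correlation (Fisher z, half-width 1.96 ÷ √40 = 0.310): 0.23 to 0.70 at r = 0.5; 0.51 to 0.83 at r = 0.7; 0.82 to 0.94 at r = 0.9.

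The planned minimum is therefore enough to give informative, if not tight, answers.

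**The case against.** The strongest reply is that the formal aim is sameness. It is worded so in the Study Summary and section 2.1, and section 1.2 speaks of comparing the PO2 values while keeping *relationship* for ISWT distance and VO2 peak. On that reading the paired t-test examines the right quantity, and the wording in sections 1.1 and 2.2 is loose narrative. This stands in part: the documents do not support a flat statement that the protocol promises a relationship and nothing else. But the text holds both wordings, the t-test does not answer the second, and non-significance does not settle the first.

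PO2 is also not a listed outcome. Section 3.2 and the Study Summary name only VO2 peak. That stands, and the point does not threaten the primary result.

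Three stronger readings are tempting and are not supported.

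- A reader might infer that end-ISWT PO2 is meant to replace end-CPET PO2 in individual patients. No section says so. Section 2.2 does foresee a test "to be used to gather helpful information about a patient's prognosis", but as a future prospect for the exercise test in general, without mention of PO2. Section 1.1 says only that end-CPET arterial PO2 predicts survival in IPF.
- A reader might infer that the t-test is uninformative about agreement. It does estimate the mean bias, which is one component of agreement, and a large bias would count against direct interchange.
- A reader might infer that worse agreement always makes rejection less likely. Step 3 holds only for a fixed non-zero mean shift. With equal means, tracking makes no difference (step 2), and where agreement is poor because of bias, rejection becomes more likely.

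**Conclusion.** The concern holds as a gap between stated questions and analysis. The PO2 question is worded in two ways. The single planned test addresses the mean within-patient difference, leaves tracking and individual differences undescribed, and cannot establish sameness through a non-significant result.

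In size: with equal true means and 43 pairs, the same non-significant result is expected about 95% of the time at correlations of 0 and 0.9, although the limits of agreement differ about threefold (2.77 ÷ 0.88 = 3.1). These widths rest on the assumed equal SDs and correlations. The insensitivity of the test to the correlation when means are equal was seen at every value tried.

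This affects an additional aim, not the VO2 peak analysis. It is worth correcting because the better analysis uses data already planned.

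**What to change.** 1. Reconcile the PO2 wording in the Study Summary and section 2.1 with that in sections 1.1 and 2.2, stating whether the question is sameness, relationship or both.
2. In section 7.5, report the mean paired difference with its 95% CI and the Bland-Altman 95% limits of agreement with CIs. Judge them against an acceptable difference that the investigators set and record before the data are seen.
3. In section 7.5, add a regression of end-CPET PO2 on end-ISWT PO2, reporting slope, intercept, correlation and residual SD with 95% CIs.
4. State that any conclusion about sameness, or about what end-ISWT PO2 says of end-CPET PO2 in a patient, will rest on items 2 and 3 and not on a non-significant t-test.

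The cost is a few sentences in the protocol, agreement on one acceptable difference, and some extra output. Section 7.4 already provides for a capillary sample after each test, so no new patients or procedures are needed.
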